6.7. Appendix 7 Adverse Events of Special Interest

From the time of local approval of protocol amendment 3 onwards, Thrombosis with Thrombocytopenia Syndrome (TTS) is considered to be an AESI.

Suspected AESIs will be recorded from the moment of vaccination until the end of the study/early withdrawal. Cases will be assessed by the Sponsor to determine the level of diagnostic certainty according to the Brighton Collaboration, CDC and PRAC requested TTS case definitions. The details for Suspected AESIs are specified in the table below.

AE Special Interest		
Category	SMQ	HLT Name
Thrombocytopenia	HAEMATOPOIETIC THROMBOCYTOPENIAS	Thrombocytopenias (HLT)
	(Sub-SMQ1) (BROAD)	
Thromboembolic	EMBOLIC AND THROMBOTIC EVENTS (SMQ)	
disorders		

6.9. Appendix 9 Multisystem Inflammatory Syndrome in Children (MIS-C)

MIS-C is a serious and potentially fatal condition that can arise in infants and children infected with SARS-CoV-2, and which can result in inflammation of a range of organs. Participants with MIS-C usually present with persistent fever, fatigue and a variety of signs and symptoms including multiorgan (eg, cardiac, gastrointestinal, renal, hematologic, dermatologic, neurologic) involvement, elevated inflammatory markers and, in severe cases, hypotension and shock.

MIS-C may present weeks after an infant is infected with SARS-CoV-2. The infant may have been infected from an asymptomatic contact and, in some cases, the infant and their parent(s)/caregiver(s) may not even know that they have been infected.

Although different presentations have been described, common symptoms include:

- Kawasaki disease-like features: conjunctivitis, red eyes; red or swollen hands and feet; rash; red cracked lips, swollen glands. Coronary artery enlargement and/or aneurysms have been described. Other symptoms include gastrointestinal (abdominal pain or diarrhea) and neurologic (headaches/meningitis) manifestations.
- Toxic shock syndrome-like features with hemodynamic instability.
- Cytokine storm/macrophage activation or hyperinflammatory features.
- Thrombosis, poor heart function, diarrhea and gastrointestinal symptoms, acute kidney injury.
- Shortness of breath suggestive of congestive heart failure.

The Center for Disease Control and Prevention (CDC 2020h) issued a Health Advisory on May 14, 2020 that outlines the following case definition for MIS-C (https://www.cdc.gov/mis-c/hcp/index.html):

Case definition for MIS-C

- An individual aged <21 years presenting with fever^r, laboratory evidence of inflammation^s, and evidence of clinically severe illness requiring hospitalization, with multisystem (≥2) organ involvement (cardiac, renal, respiratory, hematologic, gastrointestinal, dermatologic or neurological); AND
- No alternative plausible diagnoses; AND
- Positive for current or recent SARS-CoV-2 infection by RT-PCR, serology, or antigen test; or exposure to a suspected or confirmed COVID-19 case within the 4 weeks prior to the onset of symptoms.

^r *Fever >38.0°C for \geq 24 hours, or report of subjective fever lasting \geq 24 hours.

^s Including, but not limited to, one or more of the following: an elevated C-reactive protein (CRP), erythrocyte sedimentation rate (ESR), fibrinogen, procalcitonin, d-dimer levels, ferritin, lactic acid dehydrogenase (LDH), or interleukin 6 (IL-6), elevated neutrophils, reduced lymphocytes and low albumin.

Common Signs and Symptoms associated with MIS-C include the following (adapted for infants <1 year of age):

- Fever (fever $\geq 38.0^{\circ}$ C for ≥ 24 hours, or report of subjective fever lasting ≥ 24 hours)
- Vomiting
- Diarrhea
- Rash
- Bloodshot eyes
- Feeling extra tired

Note: not all infants will have the same signs and symptoms, and some infants may have symptoms that are not listed here.

Immediate **emergency care** is required in the event of the infant showing any of the following signs of MIS-C (adapted for infants <1 year of age):

- Trouble breathing
- Inability to wake or stay awake
- Bluish lips or face

Common laboratory findings include:

- An abnormal level of inflammatory markers in the blood, including elevated erythrocyte sediment rate (ESR)/C-reactive protein (CRP) and ferritin, lactate dehydrogenase (LDH).
- Lymphopenia <1000, thrombocytopenia <150,000, neutrophilia.
- Elevated B-type natriuretic peptide (BNP) or NT-proBNP (pro-BNP), hyponatremia, elevated D-dimer levels.

The following are the preferred terms for cases of MIS-C: Multisystem inflammatory syndrome, Multisystem inflammatory syndrome in children, Systemic inflammatory response syndrome, Multiple organ dysfunction syndrome, Kawasaki's disease, Toxic shock syndrome, Distributive shock, Hypotensive crisis, Vaccine associated enhanced disease, Vaccine associated enhanced respiratory disease, Cytokine release syndrome, Cytokine storm, Haemophagocytic lymphohistiocytosis, Macrophage activation, Macrophages increased, Septic shock, autoinflammatory disease.

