5.4. Secondary Endpoints Analysis

5.4.1. Definition of Endpoints

Safety and reactogenicity of Ad26.COV2.S booster vaccination in adult participants

- Solicited local and systemic AEs for 7 days after (each) vaccination, or until resolution
- Unsolicited AEs for 28 days after (each) vaccination
- SAEs and AESI throughout the study (from vaccination until end of the study, i.e. at least 12 months after delivery)
- MAAEs until 6 months after the last vaccination

• AEs leading to study discontinuation (from vaccination until end of the study)

Refer to Sections 5.6.1 for more details on adverse events definitions.

Pregnancy Outcomes

Pregnancy outcomes in adult participants (including live term birth, live preterm birth, stillbirth, and abortion). Data are captured in the Delivery History eCRF.

Pregnancy-related AEs

Pregnancy related AEs in adult participants, including gestational diabetes, gestational hypertension, premature rupture of membranes, premature labor, premature uterine contractions, poor or restricted fetal growth, pre-eclampsia, eclampsia, vaginal or intrauterine hemorrhage (non-exhaustive).

The complete list of preferred terms to be included as pregnancy related AEs is provided in Section 6.8. Refer to Sections 5.6.1 for more details on adverse events definitions.

Safety in neonates/infants

- SAEs (including Multisystem Inflammatory Syndrome in Children [MIS-C]) and AESIs in neonates/infants from birth to approximately 12 months of age.
- MAAEs for neonates/infants from birth until 6 months of age.
- AEs in neonates/infants leading to study discontinuation from birth until discontinuation.

Refer to Sections 5.6.1 for more details on adverse events definitions and Section 6.9 for MIS-C.

Neonate/infant Outcomes

Neonate/infant outcomes (including normal neonate, term neonate with (or without) complications, preterm neonate with (or without) complications, neonatal infection, respiratory distress, congenital anomalies, neonatal death, low birth weight, and small for gestational age measured from birth until approximately 12 months of age) (non-exhaustive). Data are captured in the Neonatal Medical History eCRF.

Humoral Immune Response in peripheral blood of adult participants

- Serological response to vaccination as measured by ELISA (S-ELISA; EU/mL]) at all blood collection timepoints.
- Serological response to vaccination as measured by VNA titers, 28 days after the first vaccination.

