For neonates/infants SAEs (including MIS-C), AESIs from birth until end of study (i.e., up to approximately 12 months of age), MAAEs from birth until 6 months of age (or from birth until discontinuation if the MAAE is resulting in study discontinuation) and AEs leading to study discontinuation covering the whole study period will be tabulated separately.

Listings and/or participant narratives will be provided as appropriate, for those adult participants and neonates/infants who die, discontinue study vaccinations due to an AE, or experience an SAE. All collected solicited and unsolicited adverse events will be listed.

CONFIDENTIAL – FOIA Exemptions Apply in U.S.

For all participants in the FAS-A, temperature will be summarized using the maximum of the recorded temperature per participant over the time interval up to Day 8 post primary vaccination and post-booster vaccination, where applicable. The incidences of fever will be summarized using the highest grade of fever observed for each participant using the grading system in Section 6.6.

All symptoms will be summarized taking the worst grading as captured by the investigator at Day 8 and Day 29 post vaccination and post-booster vaccination, where applicable. The number of women reporting breast milk production (reduction) from the eCOA diary data as well as the related AE will be summarized descriptively.

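### Section 6.9 prints a case definition and a broader preferred-term list for MIS-C without saying which one sets the count, so septic shock or organ failure without SARS-CoV-2 can be reported as MIS-C

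*SAP*

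**What the plan says.** SAP Section 5.4.1 places MIS-C inside the secondary safety endpoint for neonates and infants, under serious adverse events, and points to the appendix: "Refer to Sections 5.6.1 for more details on adverse events definitions and Section 6.9 for MIS-C". Section 5.6.1.3 gives the reporting rule, which begins "For neonates/infants SAEs (including MIS-C), AESIs from birth until end of study" and ends with these events being tabulated separately.

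Section 6.9 (Appendix 9) contains two descriptions of MIS-C.

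- A case definition in three parts joined by AND. The first part opens "An individual aged <21 years presenting with fever" and goes on to require laboratory inflammation and severe hospitalised illness involving at least two organ systems. The second is "No alternative plausible diagnoses; AND". The third is "Positive for current or recent SARS-CoV-2 infection by RT-PCR, serology, or antigen test; or exposure to a suspected or confirmed COVID-19 case", with exposure limited to the 4 weeks before onset.
- A list of coded terms: "The following are the preferred terms for cases of MIS-C: Multisystem inflammatory syndrome, Multisystem inflammatory syndrome in children, Systemic inflammatory response syndrome". It continues with "Multiple organ dysfunction syndrome, Kawasaki's disease, Toxic shock syndrome, Distributive shock, Hypotensive crisis" and ends with "Macrophage activation, Macrophages increased, Septic shock, autoinflammatory disease".

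No sentence in the SAP connects the list to the definition.

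**The concern.** The definition is narrow and causal: it asks for SARS-CoV-2 evidence and for other explanations to be excluded. The list is broad and descriptive. Several of its terms describe severe illness of any origin. If the table is built from the list, an infant whose shock or organ failure has a bacterial or other non-COVID cause can appear under MIS-C.

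MIS-C is the syndrome singled out by name within the infant SAE endpoint. The trial is open-label, descriptive and has no control arm (Sections 1.2 and 2), so no comparator would show that such a case is background. The same infant could also appear under neonatal infection, a separate neonatal outcome in Section 5.4.1, and so be described in two inconsistent ways. Two programmers working from this SAP could produce different MIS-C counts from the same data.

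**Working it through.** The SAP states no figure on this point, so the check compares the two rules and the places that use them.

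**1. The list against the definition.** The list has 17 terms. Two name the syndrome itself. Septic shock, systemic inflammatory response syndrome, multiple organ dysfunction syndrome, distributive shock and hypotensive crisis are severe states that need no SARS-CoV-2 evidence and exclude no other cause. Macrophages increased is a laboratory finding, and by itself it shows neither fever, nor hospitalisation, nor organ involvement.

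**2. Three constructed infants.**
- Bacterial septic shock, hospitalised, no SARS-CoV-2 infection or exposure. By the definition: the first part may be met, the second fails because the bacterial infection is an alternative diagnosis, and the third fails, so this is not a case. By the list: a hit.
- Multiple organ dysfunction with another established cause and no SARS-CoV-2 infection or exposure. By the definition: not a case, for the same two reasons. By the list: a hit.
- Sepsis coded as sepsis, without shock. By the definition: not a case. By the list: no hit, because neither sepsis nor neonatal sepsis appears on it.

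The rules disagree on the first two infants and agree on the third.

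**3. Which rule governs?** Section 5.4.1 refers to Section 6.9 as a whole, and Section 5.6.1.3 has no confirmation step. The only rule that can be run on coded data without further instruction is the list. Two comparisons within the SAP make it likely to be read as the counting rule:
- The neighbouring Appendix 8 is described in Sections 5.4.1 and 5.6.1.3 as the full set of preferred terms that count as pregnancy-related events. There, a term list is used directly for tabulation.
- For thrombosis with thrombocytopenia syndrome (TTS), Section 5.6.1.1 and Appendix 7 label the hits as suspected, send each to an adjudication committee and have cases assessed against named case definitions. MIS-C has no such wording.

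**4. How easily could a hit occur?** The SAP gives no rate for the listed terms and no number of infants. As an illustration only, let p be the non-COVID rate of any listed term and n the number of infants. The chance of at least one hit is 1 − (1 − p)^n.
- p = 0.1%: 2.2% for n = 22, 5.8% for n = 60, 21.3% for n = 240.
- p = 0.5%: 10.4%, 26.0% and 70.0%.
- p = 1%: 19.8%, 45.3% and 91.0%.

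The values of p are assumptions. The values of n are adult numbers from the SAP (the Sentinel plus Safety Cohort, a Table 1 column, and the enrolment target). Enrolment has ceased, and the number of infants is not stated. The range shows only that a hit is possible and that its chance depends on unknowns.

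**The case against.** The strongest reply is that the miscount is inferred. No sentence says that every event with a listed term is an MIS-C case. The definition has its own heading and comes first, so the list can be read as the terms under which cases may be coded, with the definition deciding which are cases. That reading is possible, but the SAP does not state it, and its own handling of Appendix 8 points the other way.

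Second, Section 5.6.1.3 names MIS-C as part of the SAE category and specifies no MIS-C rate or denominator. If infant SAEs are laid out by preferred term, septic shock would appear as septic shock. This stands as a limit on the harm, but the appendix would have no use for a term list if MIS-C were never identified as such.

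Third, the protocol is not at hand and may describe case review, and output detail is deferred to the Data Presentation Specifications. Even so, the SAP itself prints two rules that conflict and refers an endpoint to both.

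Fourth, listings and/or narratives for infants with an SAE would let a reader check each case. They would not correct the table.

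Two stronger readings are tempting and not supported. A reader might infer that ordinary neonatal sepsis is counted as MIS-C, but sepsis as such is not on the list. A reader might also size the problem by the shift in an exact upper confidence limit when one case replaces none. That would presuppose the misclassified event and use the adult target as the infant denominator. The SAP specifies Clopper-Pearson intervals under immunogenicity (Section 5.7.1), not for adverse events.

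**Conclusion.** The point holds as a gap between two rules. Section 6.9 defines MIS-C narrowly and lists terms for it broadly, and the SAP does not make the definition govern the tabulation. An infant with septic shock or organ failure and no SARS-CoV-2 infection can therefore be reported as MIS-C in the secondary infant safety endpoint. It does not follow that such an infant will be.

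The size is modest. No hypothesis is tested, no stated figure changes, and the number of affected infants is probably very small. The conclusion assumes that at least one listed term occurs without SARS-CoV-2 and that no other document settles the classification. It is still worth correcting, because one wrongly labelled case would be conspicuous in a small uncontrolled study.

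**What to change.** In Section 6.9:
- introduce the list as search terms for potential MIS-C;
- state that each hit is classified against the case definition already printed there, including the criteria on alternative diagnosis and on SARS-CoV-2 infection or exposure;
- tabulate cases that meet the definition separately from potential cases that do not.

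Add a reference to this step in Section 5.6.1.3. It follows the principle that the SAP already applies to suspected TTS.

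The cost is a few sentences and a check of the few flagged SAEs, which already receive listings and/or narratives. Infant molecular and N-serology results are already among the planned exploratory assessments (Section 5.5.1) and can inform the SARS-CoV-2 criterion.
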